2. Through the PAGs approach, IQVIA will work internally with our patient recruitment team to partner with EU PAGs to recruit potential eligible patients to participate in the quantitative study. We propose a sample size of 300 patients with cancer recruited from two European countries. This will be on a best effort basis and if 300 patients are not recruited, we will increase the recruitment using the patient panel approach. To further help supplement recruitment, the Agency will introduce IQVIA to the Agency's relevant PAG group, where IQVIA will then manage recruitment via patient panels. By utilising multiple recruitment strategies, we intent to minimize potential selection biases associated

Template No.: PCE_TP_CSC0016 Revision 2 Reference:

PCE_OP_CSC0014

Effective Date: 15Dec2019

with a single mode of recruitment and maximise the potential to make generalisable conclusions. The heterogeneity of the samples will lead to representative PP evidence for the European oncology patient population. The countries selected for the recruitment through Global Perspective will not be excluded from the recruitment strategy using PAGs.

Data Management

Qualitative Evidence Generation

⁴5 or the qualitative phase, audio-recordings obtained during the patient interviews for will be transcribed into de-identified patient transcripts and translated in English. Audio-recordings be automatically deleted when transcription is completed. De-identified transcripts will be stored in an encrypted IQVIA server in a password-protected file, accessible only to specific study staff.

Quantitative Evidence Generation

For the quantitative phase, eligible patients will be invited to participate and if interested, will complete an online consent, which will give them access to the PP survey. Patients will be requested to complete the choice sets, by indicating their preferred alternative for each scenario. The online platform where the data collected will be automatically stored, Qualtrics^{XM}, will allow for real-time review of the data for quality and completeness. Access to the database will be restricted with a username and password to key members of the research team.

Data will be validated as defined in the summarized Data Management Plan. Quality control procedures will be applied to ensure all the online data collected via the survey platform corresponds to the final survey and to eliminate potential missing, out of range, illogical or erroneous data.

A pilot phase will be conducted with 20 patients. Based on the feedback from the pilot-testing, modifications to the online survey will be made to finalize the electronic migration. No concurrent manual data review will be performed, and no queries will be followed up with patients for resolution.

High data quality standards will be maintained, and processes and procedures will be utilized to repeatedly ensure that the data are as clean and accurate as possible when presented for analysis. When all data have been validated, signed and locked, the data file will be declared as being a clean file. The final database will then be locked.

Template No.: PCE_TP_CSC0016 Revision 2 Reference:

PCE_OP_CSC0014

Effective Date: 15Dec2019

File Retention and Archiving

To enable evaluations and/or audits, all records, including source documents and adequate documentation of relevant correspondence (e.g., letters, meeting minutes, telephone calls reports) will be kept in IQVIA's secure servers. The records will be retained according to local regulations, or as specified in the study contract, whichever is longer.

All records will be kept and made available for review in the event of audits, or inspections and will be safely archived for at least 5 years after the completion of the study.

Monitoring and Reporting of AE / SAE

4 The sponsor will follow standard procedures for handling adverse events reporting involving these patients – specifically, reporting adverse events to drug safety.

In the event that the patient reports intent or actual harm to themselves or others, IQVIA will ask for the clinician contact during the interview and will report the incident to the patient's clinician or a local suicidal/crisis center to the best their capabilities.

5. Data Analysis

The sample for both phases will be described by means, standard deviations, median, and range, for continuous variables, and by number and proportion of the total study population for categorical ones. 5.1.

Qualitative Evidence Generation Analyses

To assess the face and content validity of the survey, vignettes, attributes and associated-levels, the data obtained from the interviews and the pilot will be assessed and coded thematically for analysis, and issues arising in relation to vignette content or format will be extracted and used for revision towards the final survey. Patient verbatim will be coded to examine comprehension, relevance, and ease or difficulty of selecting a response. The overall goal of coding these data is to facilitate the identification of concepts that are most important and relevant to patients. The coding process identifies and categorizes patient concept expressions. Coders review each transcript to identify text that includes concept expressions, and tags selected text with a code. The codes are organized within a coding framework, which is established at the beginning of the process and refined/expanded during the coding process. Once the coding process has been

Template No.: PCE_TP_CSC0016 Revision 2 Reference:

PCE_OP_CSC0014

Effective Date: 15Dec2019

completed, outputs are generated in tabular, graphical, or text formats to summarize results in WORD or PowerPoint reports. All interview transcripts (PDF format) will be included as appendices to the final report or in supplemental electronic files. Content within and between vignettes will be further compared and examined for comprehension and ease or difficulty of selecting a response.

For the qualitative phase, all data will be described using Atlas.ti® version 7 or higher and Microsoft® Excel.

Quantitative Evidence Generation Analyses

Primary Analysis

5.2. The final analyses will be fully described in the statistical analysis plan and will depend on the stated preference methodology used. Continuous variables will be described by mean, standard deviation (SD), 95% confidence intervals (CI), median, 25th and 75th percentiles, minimum and maximum. Categorical variables will be described by frequencies and related percentages of the study population, and by subgroups.

The primary objective is aimed at identifying and describing the cancer PP about benefits and harms of cancer drugs and to understand the trade-offs between factors leading to PP with the main method, DCE. For this objective, we propose using Bayesian multinomial logistic regression (MNL) models reporting odds ratio's and 95% confidence intervals. Attribute-levels will be estimated relative to a reference level for each attribute. The reference level will be selected based on the attribute-level having the lowest parameter estimate. The analysis of preferences of patients towards a treatment will allow us to investigate which attributes (and levels) influence patient choices for selecting the most appropriate treatment for patients with various cancers. A Bayesian MNL model computes the best fitting estimates via utility estimation to account for the overall pattern of choices reported by the patients. Results from utility estimation allows for the estimation of coefficients for each attribute-level, with a positive parameter in the model representing a positive utility associated with a particular attribute-level, whereas a negative parameter in the model represents disutility associated with a particular attribute-level. Using a Bayesian MNL model, the coefficients for the different attribute-levels can then be combined to allow for investigation of these factors when making a treatment decision. [41]

The relative importance of the attributes that are relevant to the patients' preference for selecting treatment will be also assessed depending of the stated preference method used. Generally,

Template No.: PCE TP CSC0016 Revision 2 Reference:

PCE OP CSC0014

Effective Date: 15Dec2019

mean part-worth utility values for each attribute will be estimated using the Bayesian MNL models for the main method DCE. Part-worths will be scaled and normalized to allow for comparisons to assess the relative importance of the attributes from most important to least important. The reference factor level will be set to the least important value for each attribute. The factor level with the largest part-worth (in absolute value) would also represent the impact of that attribute it belongs to.^[45] The relative importance of the attributes will be described in related percentages.

To complement the analysis for this primary objective, cancer PP about the benefits and harms of cancer therapies and the different trade-offs between factors will also be examined using MCDA and TTO methodologies with a smaller subset of patients. For the MCDA method, partial value functions will be elicited using the additive value model. Ratings of the alternatives will be described, along with the sum of the preference weights to account for relative importance, using frequencies and related percentages. The sum and spread of the weights will be described using a non-linear curve representing the average weights as a function of the ratings. For the TTO method, regression analysis will be applied to estimate utility values by dividing the number of years corresponding to the patient's choices for a treatment by 10 (years). The patient's preferences with different treatments will be measured in units of quality of life differences between the two treatment options, and the utility values (mean, SD, 95% confidence intervals) will range between 0 and 1.

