patients, and confirmation of diagnosis will be obtained by Global Perspective using either a diagnosis prescription picture or a treatment prescription picture. Patients who are eligible based on the completion of the screener and agree to participate will be contacted to obtain electronic consent and will consequently have an interview scheduled.

Quantitative Evidence Generation

Approximately 900 adult patients with cancer will be recruited to participate in the quantitative phase of the study using a combination of both patient panels and patient advocacy groups (PAGS).

1. With the patient panel approach, IQVIA will work with Global Perspective to recruit potential eligible patients with cancer to participate in the quantitative phase of the study. Similar to the qualitative evidence generation phase, patients who would like to join the panel will be requested to complete a profiling survey where they will be asked several socio-demographic and healthcare questions so the panel can pre-target the patients as having a certain condition (e.g. NSCLC) and being part of a certain socio-demographic background. We propose a sample size of 300 patients with cancer recruited each from Spain (Western Europe) and Poland (Eastern Europe) (total = 600 patients) to have a better balance of different regions of Europe that may differ in terms of oncology treatment practices, and ensure heterogeneity in patients with cancer from different parts of Europe.

Global Perspectives will invite potential eligible patients to participate in the qualitative and quantitative phases of the study. A screener will be developed by IQVIA to help identify eligible patients, and confirmation of diagnosis will be obtained by Global Perspective using either a diagnosis prescription picture or a treatment prescription picture. Patients who are eligible based on the completion of the screener and agree to participate will be sent a link via email to the survey. The anonymized data will be automatically saved to the data management platform.

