 - Burden to the patient: Reflecting on and trading off different treatment attributes of relevance may be overly cognitively burdensome to the patient. To minimize this risk, feedback on the qualitative interviews and identification of the attributes will be assessed using cognitive debriefing techniques.

7.2.2.

Quantitative Evidence Generation

• Information bias: As with collection of all self-report data, there is a possibility that patients may give inaccurate responses based on the method of survey administration. Using an anonymized online survey may reduce this type of bias compared to interview-based methods as risk of social desirability bias is minimized in the absence of a researcher, and in the knowledge that responses will not be linked back to individuals. This will be emphasized in the survey instructions to encourage accurate and truthful responses from

Template No.: PCE TP CSC0016 Revision 2 Reference:

PCE_OP_CSC0014

Effective Date: 15Dec2019

patients in this phase of the study. However, self-reported preferences may still differ from observed or actual preferences for reasons that cannot be controlled for in this study

- Selection bias: Study participation is voluntary, and the sample of patients recruited could
 differ those from the general population. Efforts will be made to ensure the recruitment of
 patients is as generalizable as possible. Information will be retained on patients not
 meeting selection criteria for enrollment. Patient characteristics will also be fully described
 as per the patient screener.
- Attributes identified and captured in the current study: There may be treatment attributes and factors outside of the current study that are important to patients but were not identified and represented in this study. There is also the risk that patients may not relate or understand certain attributes. Our attributes and associated-levels in the preference survey will be based on the targeted literature review and feedback received from patients during the qualitative evidence generation interviews. To minimize this risk, relative importance of attributes and associated-levels will be assessed. Patients will also be asked questions on how well the patients understood the attributes described in the choice tasks.
- Burden to the patient: The administration of the different PP methodologies and trading
 off different treatment attributes of relevance may be overly cognitively burdensome to the

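### The protocol promises representative European evidence from a volunteer sample that cannot provide it, and describes a diagnosis check for only one of its two recruitment routes

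*Protocol*

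**What the plan says.** Section 4.2.3 (Patient Recruitment), under Quantitative Evidence Generation, builds the survey sample from two routes, one through panels and one through advocacy organisations. The target reads: "Approximately 900 adult patients with cancer will be recruited to participate in the quantitative phase of the study using a combination of both patient panels".

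- Panel route: "300 patients with cancer recruited each from Spain (Western Europe) and Poland (Eastern Europe) (total = 600 patients").
- Advocacy route: "We propose a sample size of 300 patients with cancer recruited from two European countries". The two countries are not named. On a shortfall: "This will be on a best effort basis and if 300 patients are not recruited, we will increase the recruitment using the patient panel approach".
- Overlap between the routes: "The countries selected for the recruitment through Global Perspective will not be excluded from the recruitment strategy using PAGs".

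The section argues that using several strategies limits the selection bias of any single one, and concludes that "The heterogeneity of the samples will lead to representative PP evidence for the European oncology patient population".

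On eligibility, the panel paragraph says that "confirmation of diagnosis will be obtained by Global Perspective using either a diagnosis prescription picture or a treatment prescription picture". The advocacy paragraph has no matching step. Section 4.2.1 requires a cancer diagnosis of every patient but does not say how it is shown.

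Under selection bias, Section 7.2.2 says: "Study participation is voluntary, and the sample of patients recruited could" differ from the general population. Section 5.2.2.1 gives country as one example of a variable to be interacted with the attribute levels.

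**The concern.** A mixed sample is not a representative one. Representativeness needs a known relation between the sample and the target population, such as a sampling frame with known selection probabilities, or at least a weighting scheme with a defensible basis. Here the claim rests on heterogeneity alone. Section 8 says the results are meant to inform regulatory thinking on efficacy and safety endpoints, so a reader may carry preference weights over to European patients with cancer in general.

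Two features of recruitment add to this. The described proof of diagnosis stops at the panel route, so the two parts of the sample may not be equally secure on the central eligibility criterion. And because the advocacy countries are left open, the study may end with each country reached by one route only. A difference between, say, an advocacy country and Poland could then reflect the country, the kind of person who joins an advocacy group, or both.

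**Working it through.** **1. The plan's own total.** Inputs from Section 4.2.3: 300 (Spain, panel) + 300 (Poland, panel) + 300 (advocacy) = 900. The stated figure is reproduced.

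**2. The claim set beside the design.**

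- Countries: two panel countries plus two advocacy countries gives at most four as planned. If advocacy recruitment fails entirely, the panel route fills the gap, and only Spain and Poland are named for it.
- Entry: panel members arrive through marketing, social media or referral (Section 4.2.3), and all respondents need internet access and an email address (Section 4.2.1).
- Frame and weights: none described.
- Limitation: Section 7.2.2 acknowledges that volunteers may differ and offers only efforts towards generalisability.

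The sentence in Section 4.2.3 asserts as an outcome what Section 7.2.2 treats as uncertain. The two do not agree.

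**3. Patients by a route with no described diagnosis check.** If k advocacy patients are recruited and panels fill the rest, the share is k/900.

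- k = 300: 300/900 = 33%
- k = 100: 100/900 = 11%
- k = 0: 0%

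This is a range of exposure, not a count of unverified patients. The protocol does not say that advocacy patients go unchecked, and the stream introduced by the Agency is described as managed through panels.

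**4. Country and source.** Suppose a mean preference score is the sum of a country effect and a source effect.

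- Spain minus Poland, both panel: the source effect cancels.
- Advocacy country minus panel country: country difference plus source difference.

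With no shared country, the model has an intercept, three country indicators and one source indicator, which is 5 parameters. The source indicator equals the sum of the two advocacy-country indicators, so the rank is 4 and source cannot be estimated apart from country.

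For the alternatives, assume 150 advocacy patients per country, a score with SD 1, two-sided 5% and 80% power (multiplier 1.96 + 0.84 = 2.80). The protocol gives none of these analysis values.

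| Shared countries | Distinct countries | Parameters / rank | SE of source effect | Detectable difference |
|---|---|---|---|---|
| None | 4 | 5 / 4 | not estimable | none |
| One | 3 | 4 / 4 | √(1/300 + 1/150) = 0.100 SD | 2.80 × 0.100 = 0.28 SD |
| Both | 2 | 3 / 3 | √(0.010/2) = 0.071 SD | 2.80 × 0.071 = 0.20 SD |

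If both are shared but only 50 advocacy patients are found (25 per country, with panels filled to 425 per country), the SE is √[(1/425 + 1/25)/2] = 0.146 SD and the detectable difference is 0.41 SD. With one shared country, the source effect is learned there and carried to the others, which assumes that it is the same in each country.

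**The case against.** The strongest reply is that the limitation is already disclosed. Section 7.2.2 names selection bias and promises a full description of patient characteristics. Recruitment is not haphazard either: there are targets of 300 per stream, and panels pre-target by condition and background. So it would be wrong to say that the plan has no quotas. This stands, but such targets are not a sampling frame, and the disclosure sharpens the conflict with the unqualified sentence in Section 4.2.3.

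Second, the analysis is deferred to the statistical analysis plan (Section 5.2), and the interaction variables are given only as examples. This also stands. The absence of a source term from the protocol is not a fault, and weighting may be planned elsewhere. But no analysis can recover a contrast that recruitment never created, and weighting on measured characteristics would not remove volunteer selection.

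Third, a reader might infer that a third of the sample is unverified. That turns silence into fact; 33% is only the upper bound. Section 7.3.1 does mention review of medical records, but as general confidentiality text and not as a diagnosis check. Data Management foresees no concurrent manual review and no queries to patients, so a later catch is not evident.

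Fourth, a reader might infer that country effects as a whole cannot be interpreted. They can in part. Spain and Poland are both panel samples, and theirs is the Western-Eastern comparison that the section sets up. The two advocacy countries can likewise be compared with each other. Aliasing affects only contrasts across routes, and only if no country is shared.

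**Conclusion.** The point holds in a limited form. The representativeness sentence claims a property that the design lacks and conflicts with Section 7.2.2. This does not depend on any assumption about the unseen analysis plan, because heterogeneity of a volunteer sample does not establish representativeness.

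The diagnosis gap is one of description: 0 to 300 of 900 patients could come by a route with no stated check. The documents give no basis for the direction or size of any effect on the preference estimates.

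The source-country problem is conditional. It arises if neither advocacy country is Spain or Poland, and it then affects contrasts between advocacy and panel countries only. The SD-scale figures rest on the assumed 5% level, 80% power, equal split of advocacy patients and additive effects. They show what overlap would buy and are not the precision of the planned choice model.

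**What to change.** - Delete the representativeness sentence, or qualify it to agree with Section 7.2.2 and limit conclusions to the volunteers recruited.
- Apply the panel's confirmation of diagnosis to advocacy patients. If that is not feasible, show the primary discrete choice result also without unconfirmed patients.
- Record recruitment source for every respondent. Base the Spain-Poland contrast on panel patients.
- State that contrasts between a panel country and an advocacy country will not be read as country effects unless at least one country is recruited by both routes.

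Overlap is a trade-off and not a free gain: with two advocacy countries, sharing one reduces the study from four countries to three, and sharing both reduces it to two. Full overlap is therefore not recommended as a requirement. Post-stratification is not a substitute, since it needs outside population figures and leaves volunteer selection in place.

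The cost is a few sentences, one data field and possibly one supplementary analysis. Advocacy recruitment may run slightly slower, and the claim of generality becomes more modest.

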Approximately 900 adult patients with cancer will be recruited to participate and complete a web-based preference survey to understand their treatment choices and treatment heterogeneity. Saragle size recommendations depend on the number of attributes and levels of each attribute included. Johnson and Orme [41, 42] suggest that the sample size required for assessing main effects depends on the number of choice tasks (t), number of alternatives (a) and the number of analysis cells (c) equal to the largest number of levels for any of the attributes: $N > 500c / (t \times a)$. Recently findings show that precision of preference estimates increase at sample sizes just below 150 respondents. Most studies estimating PP include approximatively 100 - 250 respondents per country. Given the number of attributes and the potential interactions to examine differences in task and heterogeneity, a larger sample size is warranted. We estimated the proposed sample size of approximately 900 patients will be sufficient to estimate preferences and to account for heterogeneity. In order to participate in this part of the study, patients must meet all of the eligibility criteria.

4.2.3.

Patient Recruitment

4.2.3.1.

Qualitative Evidence Generation

Approximately 30 adult patients with cancer will be recruited to participate in the qualitative interviews through patient panels. IQVIA will work with Global Perspective, our external patient recruitment partner, to recruit potential eligible patients to participate in the qualitative evidence generation phase of the study. The panel teams are from different sources, including marketing campaign targeting, social media, or through a referring process (such as by physicians or patients directly). Patients who would like to join the panel will be requested to complete a profiling survey where they will be asked several socio-demographic and healthcare questions so the panel can pre-target the patients as having a certain condition (e.g. NSCLC) and being part of a certain socio-demographic background.

Global Perspectives will invite potential eligible patients to participate in the qualitative evidence generation phase of the study. A screener will be developed by IQVIA to help identify eligible

Template No.: PCE_TP_CSC0016 Revision 2

Reference:

PCE_OP_CSC0014

Effective Date: 15Dec2019

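### The DCE reference level is the level with the lowest estimate, so every point odds ratio is forced to 1 or above and weak attributes are biased upward

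*Protocol*

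**What the plan says.** Protocol Section 5.2, Primary Analysis, plans Bayesian multinomial logit models for the discrete choice experiment (DCE), "reporting odds ratio's and 95% confidence intervals". The contrasts are defined in the same paragraph: "Attribute-levels will be estimated relative to a reference level for each attribute". The reference is then chosen by this rule: "The reference level will be selected based on the attribute-level having the lowest parameter estimate". That paragraph goes on to say how signs will be read, including that "a negative parameter in the model represents disutility associated with a particular attribute-level".

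The next paragraph, on relative importance, states the reference again in other terms: "The reference factor level will be set to the least important value for each attribute". It adds: "The factor level with the largest part-worth (in absolute value) would also represent the impact of that attribute it belongs to".

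The section leaves the full analysis to the statistical analysis plan. The reference rule itself, however, is stated here.

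**The concern.** A parameter estimate is model output. Choosing the lowest one as baseline therefore means choosing the comparator after seeing the results, then reporting the other levels against it with ordinary 95% intervals that take no account of the choice. Two things follow.

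- **Internal conflict.** If the lowest level is always the reference, no reported level coefficient can be negative. The sentence on disutility, and the use of absolute values for the largest part-worth, then have nothing to act on. Least important is also not the same criterion as lowest estimate, and it is not defined for a level. If it means the part-worth closest to zero under effects coding, it would often select a middle level, and coefficients of both signs would appear.
- **Selection bias.** Where the levels of an attribute hardly differ, the level that is lowest by chance becomes the baseline and every other level looks better than it. The section aims to learn which attributes and levels influence choices, so a false exclusion of 1 bears on the primary objective.

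**Working it through.** The protocol gives no figure for the effect of this rule, so there is none to reproduce. It also fixes neither the number of levels per attribute nor the number of choice tasks, so both are assumptions below.

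**Inputs**
- From the protocol: the rule, the contrasts, 95% intervals (critical value 1.96), two alternatives per task, about 900 patients.
- Assumed: L = 2 to 5 levels; an attribute with no effect; independent, equal-variance level estimates; near-flat priors; 10 tasks for the absolute size.

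**1. Sign.** Let b_j be the estimate for level j. The reported contrast is b_j − min(b), which is never below 0, so every point odds ratio is at least 1. This is algebra, not chance. Interval limits can still fall below 1.

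**2. Mean contrast when the truth is 0.** Take level estimates with unit variance, so a contrast has standard error √2. The average over the non-reference levels, in standard errors, is [L/(L−1)] × E(max)/√2, where E(max) is the expected maximum of L standard normals.
- L = 2: 2 × 0.564/1.414 = 0.80
- L = 3: 1.5 × 0.846/1.414 = 0.90
- L = 4: 1.333 × 1.029/1.414 = 0.97
- L = 5: 1.25 × 1.163/1.414 = 1.03

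With a reference fixed in advance it is 0.

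**3. False exclusions of 1.** Put c = 1.96 × √2, with φ and Φ the standard normal density and distribution function; integrals run over m.
- Lowest-estimate reference, any contrast: 1 − L∫φ(m)[Φ(m+c) − Φ(m)]^(L−1) dm
- Fixed reference, any contrast: 1 − ∫φ(m)[Φ(m+c) − Φ(m−c)]^(L−1) dm
- Lowest-estimate reference, per contrast: L∫φ(m)[1 − Φ(m+c)][1 − Φ(m)]^(L−2) dm

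| Levels | Any, lowest-estimate | Any, fixed | Per contrast, lowest-estimate | Per contrast, fixed |
|---|---|---|---|---|
| 2 | 5.0% | 5.0% | 5.0% | 5.0% |
| 3 | 12.2% | 9.1% | 6.8% | 5.0% |
| 4 | 20.3% | 12.5% | 8.4% | 5.0% |
| 5 | 28.6% | 15.6% | 9.7% | 5.0% |

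A simulation of 400,000 draws agrees to within about 0.1 percentage point. The excess due to the rule is the difference between the two columns for any contrast: 3.1, 7.8 and 13.0 points for 3, 4 and 5 levels. What remains with a fixed reference is ordinary multiplicity from several contrasts.

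**4. Absolute size at 900 patients.** Two-alternative choices were simulated with five attributes (ranges 1.0, 0.6, 0.6, 0.3 and 0 on the log-odds scale), 10 tasks per patient, and maximum likelihood fits. The mean largest odds ratio for the null attribute was 1.05 with 3 levels and 1.07 with 4. Hand check for 3 levels: the expected range is 2 × 0.846/1.414 = 1.20 standard errors. With a standard error of about 0.040, exp(1.20 × 0.040) = 1.05.

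**The case against.** The strongest reply is that the rule is mostly harmless here. Attributes enter the survey only after interviews have shown them to matter, and the candidates named in the protocol (progression-free survival, overall survival, safety) have a natural order. With a range of 0.3 over three evenly spaced levels, adjacent levels differ by 0.15. At a standard error of 0.040 the two levels swap order with probability 1 − Φ(0.15/0.040) = 1 − Φ(3.75), about 0.0001. The rule then picks the least favourable level, which is what a sensible prespecification would name. This stands for strong ordered attributes, but not for weak or unordered ones.

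It can also be said that the objective is descriptive, that no significance test is set, that changing the reference leaves model fit and utility differences unchanged under near-flat priors, and that the sentence on negative parameters is a general explanation. All fair. Even so, the protocol promises 95% intervals on these contrasts, and they will be read against 1. Nor does it say whether the estimates come from the main data, the 20-patient pilot or prior expectation; the main data is the natural reading, not a stated fact.

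Three stronger readings are tempting and are not supported.

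- A reader might infer that the rule inflates attribute importance. A highest-minus-lowest range does not depend on the reference, and the largest absolute part-worth of a null attribute is positive under any fixed reference. In the simulation at 900 patients, null importance was 1.8% under the rule and 1.6% with a fixed reference (3 levels), and 2.5% and 2.1% (4 levels). Roughly 85 to 90% of it would remain after the fix.
- A reader might infer subgroup artefacts from references that differ between groups. The Secondary Analysis plans interactions of attribute levels with patient characteristics, not separate fits with a reference chosen afresh in each group.
- A reader might set the rates for any contrast against 5%. The like-for-like comparator is a fixed reference with the same number of contrasts.

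**Conclusion.** The rule is wrong as written. Applied to the main-study estimates, it forces all point odds ratios to 1 or above, conflicts with the section's own reading of negative parameters, and sits beside a second, different reference criterion. For attributes with no effect it shifts the reported log odds ratios upward by about 0.8 to 1.0 standard errors on average. With 3 or more levels, the 95% intervals exclude 1 more often than they should. With 2 levels only the direction is forced and the exclusion rate stays at 5%.

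The practical harm is confined to weak or unordered attributes and is modest at the planned sample size. The figures rest on independent, equal-variance level estimates and near-flat priors, and the absolute size also on 10 tasks and the assumed effect sizes. The sign constraint and the conflict in wording need none of these assumptions, only that the reference is the lowest of the reported estimates.

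**What to change.** Delete the lowest-estimate rule. Name one reference level for each attribute before any data are seen, for example the expected least favourable level, and keep it the same in all analyses; or use effects coding. Replace the two reference statements in Section 5.2 with that single definition, so that the text on negative parameters and absolute part-worths agrees with it.

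The cost is about one sentence in the protocol, carried into the statistical analysis plan. The one downside is that some coefficients may turn out negative, which is informative and which the section already explains how to read.
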